1. Mini Mental State Assessment Test: The Mini Mental State Assessment (MMSA) is a common screening tool to systematically and comprehensively assess individuals' cognitive status. The test consists of 11 items assessing five cognitive domains: orientation, registration, attention and calculation, recall, and language. The maximum score that can be obtained from the scale is 30, and scores of 23 or below suggest cognitive impairment. The administration time, approximately 5–10 minutes, makes the tool suitable for routine use in clinical and research settings. Its validity and reliability in Turkish were conducted.

2. Personal Information Form: The questionnaire, which included the participants' descriptive and clinical characteristics, was developed by the researchers in two sections based on literature and clinical observations. The first section consisted of seven questions covering the patient's descriptive characteristics, including age, gender, and education level, in line with the study group, and the patient's clinical characteristics, including diagnosis, preoperative fasting time, postoperative oral intake time, and the time to start oral intake. The second section included a chart created for recording bowel sounds.

3. Surgical Period Thirst Discomfort Scale (SPTDS): The original seven-item scale was removed due to the low factor analysis of one item in the Turkish validity and reliability study. It was adapted as six items using a three-item Likert-type scale. Ratings are as follows: "Didn't Bother (0)," "A Little Bit Bothered (1), and "A Lot Bothered (2). The scale items are: "My Mouth is Dry," "My Lips are Dry," "My Saliva is Thick," "My Throat is Dry," "I Have a Bad Taste in My Mouth," and "I Want to Drink Water." The minimum score for the total scale is 0, and the maximum score is 12. As the score obtained from the scale increases, the level of discomfort related to thirst also increases.

4. Comfort Level Determination Scale - VAS: The comfort level of the individuals participating in the study will be determined using the Visual Analog Scale-10 (VAS-10). The scale is a 10-cm straight line with points spaced 1 cm apart. Each point on this straight line will be evaluated as a score for the comfort level, with the starting point being "0 = Lowest Comfort Level" and "10 = Highest Comfort Level." As the score obtained from the scale increases, the comfort level also increases.

Intervention Procedure

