Before initiating the main study, a pilot application was conducted with a total of eight patients—four from the experimental group and four from the control group—to evaluate the data collection instruments and the implementation process. The results of the pilot study indicated that all scale items were found to be clear and understandable by the participants, and the average response time ranged between 10 and 12 minutes. No technical or logistical problems were encountered during the process, and the main study was subsequently initiated. Data obtained from the pilot study were not included in the main sample.

During the pilot phase, data collection instruments were administered to the experimental group patients after each oral rinse. However, as patients provided near-perfect responses across all measurements, a potential risk of bias was identified. Therefore, in the main study, the data collection instruments were administered only before the first oral rinse and after the completion of all three rinses.

The purpose of the study was explained to all participants, and written informed consent was obtained. Data were collected face-to-face by the researchers.

In the experimental group, postoperative cognitive assessment was conducted, and patients scoring 23 or higher on the MMSE (Mini-Mental State Examination) were instructed to perform oral rinsing three times at 20-minute intervals, each time using 20 ml of distilled water. Two graduated plastic cups were used for each rinsing: one containing 20 ml of distilled water and one empty cup for spitting out the rinse water. This setup enabled the evaluation of whether patients swallowed the water; none of the patients did, and all participated in the procedure compliantly. Data collection forms were administered face-to-face before the first rinse and 15 minutes after the final rinse, and bowel sounds were auscultated.

In the control group, postoperative cognitive assessment was also conducted, and patients scoring 23 or higher on the MMSE were administered the data collection forms and had their bowel sounds auscultated. No intervention was applied to this group. The data collection forms were re-administered 75 minutes later, in a manner consistent with the experimental group, and bowel sounds were re-evaluated.

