To ensure consistency and avoid inter- or intra-group differences, all bowel sound assessments were performed using the same brand and model of stethoscope, and each patient's bowel sounds were auscultated for one minute. Considering the oral rinsing process, the total time required for data collection in the experimental group was approximately 20–25 minutes.

Data Analysis

SPSS 22.00 package program was used to analyze the data. Skewness-Kurtosis analyses were performed to determine the conformity of the data to a normal distribution. A Skewness-Kurtosis value between +1.96 and -1.96 is considered a normal distribution. All data used in the study were within the normal range, and the data showed a normal distribution. Frequency (n) and percentage (%) distributions were calculated to determine the sociodemographic and clinical characteristics of the participants. A t-test for independent samples was used to determine the mean differences between two independent groups, a t-test for dependent samples was used to compare pre- and post-intervention measurements, and a single-factor analysis of variance (ANOVA) was used for repeated measures. Cohen's d effect size was calculated to assess the significance of the difference between the groups in terms of the intervention. Statistical significance was accepted as $p<0.05$.

RESULTS

The mean age of the participants in the experimental group was 56.41 ± 14.80 years, while in the control group it was 55.78 ± 14.00 years. Overall, 57.1% of the participants were female. Among the patients, 46.9% of those in the experimental group and 42.9% in the control group were primary school graduates.

Clinically, 49% of the patients underwent surgery for cholecystectomy. The preoperative fasting period ranged between 7–18 hours in the experimental group, with a mean of 11.78 ± 2.47 hours, and between 8–36 hours in the control group, with a mean of 12.78 ± 4.33 hours.

The postoperative oral intake initiation time in the experimental group ranged between 6–20 hours, with a mean of 10.41 ± 4.64 hours, while in the control group it ranged between 2–66 hours, with a mean of 15.20 ± 11.57 hours. The

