Within-group comparisons showed that in the experimental group, post-rinsing measurements demonstrated an increase in comfort level, a decrease in thirst-related discomfort, and an increase in bowel motility compared to pre-rinsing values. In contrast, no significant changes were observed between the two measurements in the control group.

These findings indicate that oral rinsing led to significant improvements in comfort, reduction of thirst-related discomfort, and stimulation of bowel motility in the experimental group, while no meaningful changes occurred in the control group.

CONCLUSION

In conclusion, oral rinsing with plain water is an effective, cost-free, and easily applicable method for reducing postoperative thirst discomfort, enhancing comfort, and accelerating bowel movements. It is recommended that this practice be integrated into routine care in surgical clinics.

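### Does re-assessing controls at 75 minutes spoil the comparison with the experimental arm's post-test?

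*Combined protocol and SAP*

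**What the plan says.** All the timing statements but two come from the Intervention Procedure section.

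- Experimental arm: patients were "instructed to perform oral rinsing three times at 20-minute intervals", and the forms were given "before the first rinse and 15 minutes after the final rinse".
- Control arm: "The data collection forms were re-administered 75 minutes later, in a manner consistent with the experimental group". Forms and auscultation come first in the description, and both are then repeated.
- Durations: in the eight-patient pilot, "the average response time ranged between 10 and 12 minutes". At each assessment, "bowel sounds were auscultated for one minute".
- Overall time: "the total time required for data collection in the experimental group was approximately 20–25 minutes".

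Data Collection Tools adds one duration, for the cognitive test: "The administration time, approximately 5–10 minutes". The Results section adds that "no significant changes were observed between the two measurements in the control group".

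The document does not state the wait between pre-test and first rinse, the length of a rinse, whether the 20 minutes run from start to start or from end to start, or when the 75-minute clock begins.

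**The concern.** Three events spaced 20 minutes apart contain two gaps. On the ordinary reading the last rinse falls at 40 minutes and the post-test at 55, yet controls wait 75. The text presents the two schedules as matching and does not show how 75 was obtained.

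The main comparison sets the second measurement in one arm against the second measurement in the other, and it needs a common interval. If untreated patients become thirstier and less comfortable as time passes, a later control measurement makes rinsing look better than it is. All three control means did move that way: thirst discomfort rose, comfort fell and bowel sounds fell. The overall figure of 20–25 minutes adds to the doubt, because it cannot be the elapsed time of a schedule lasting at least 55 minutes.

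**Working it through.** **Inputs.** Three rinses, 20-minute spacing, 15-minute wait, 75-minute control interval, 10–12 minutes of response time and 1 minute of auscultation (Intervention Procedure); 5–10 minutes for the cognitive test (Data Collection Tools); 49 patients per arm (Study Population and Sample); means, SDs and t values (Results).

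**Reproducing the 75 minutes.**

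- Three full intervals plus the wait: 3 × 20 + 15 = 75. This matches exactly and fits the text if there was a 20-minute wait before the first rinse.
- From the first rinse, counting two gaps: 2 × 20 + 15 = 55, which is 20 short.
- From the start of the pre-test, taking the pilot response time as its length and allowing nothing for rinsing or waiting: 55 + 10 + 1 = 66 to 55 + 12 + 1 = 68, which is 7 to 9 short. Rinses of (75 − 68)/3 = 2.3 to (75 − 66)/3 = 3.0 minutes each, added to the intervals, would close that gap.
- From the start of the cognitive test: 66 + 5 = 71 to 68 + 10 = 78, a range that contains 75.

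The possible excess of the control interval is therefore 0 to 20 minutes, depending on unstated details.

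**The 20–25 minutes.** Two form administrations and two auscultations take 2 × 10 + 2 × 1 = 22 to 2 × 12 + 2 × 1 = 26 minutes. The figure is close to staff contact time and need not contradict the schedule.

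**What 20 minutes could be worth.** Take the control change over 75 minutes and scale it by 20/75, which assumes linear drift. For an unfavourable bound, use the 95% limit of the control change:

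limit = |change| + 2.011 × √(s₀² + s₁² − 2·r·s₀·s₁)/√49

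Here 2.011 is the t quantile on 48 degrees of freedom. The pre-post correlation r is not reported and is assumed to lie between 0 and 0.8. For thirst discomfort at r = 0: 0.45 + 2.011 × √(2.74² + 2.15²)/7 = 0.45 + 1.00 = 1.45.

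| | Thirst discomfort | Comfort | Bowel sounds |
|---|---|---|---|
| Control change | 8.59 − 8.14 = +0.45 | 3.86 − 4.02 = −0.16 | 3.86 − 4.06 = −0.20 |
| Size over 20 min | 0.12 | 0.04 | 0.05 |
| Difference between arms | 8.59 − 1.31 = 7.28 | 7.33 − 3.86 = 3.47 | 5.98 − 3.86 = 2.12 |
| Share of difference | 1.6% | 1.2% | 2.5% |
| 95% limit of change, r = 0.8 to 0 | 0.92 to 1.45 | 0.48 to 0.72 | 0.46 to 0.76 |
| Limit × 20/75 | 0.25 to 0.39 | 0.13 to 0.19 | 0.12 to 0.20 |
| Share of difference | 3–5% | 4–6% | 6–10% |

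At an excess of 7 to 9 minutes the linear drift is 0.04 to 0.05, 0.01 to 0.02 and about 0.02.

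**Effect on the tests.** Subtract the largest 20-minute figure from each difference and hold the standard error fixed:

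- Thirst discomfort: 19.269 × (7.28 − 0.39)/7.28 = 18.2
- Comfort: 16.438 × (3.47 − 0.19)/3.47 = 15.5
- Bowel sounds: 7.334 × (2.12 − 0.20)/2.12 = 6.6

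**Dropping linearity.** Suppose the whole control change, at its unfavourable limit with r = 0, fell within the disputed 20 minutes:

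- Thirst discomfort: 19.269 × (7.28 − 1.45)/7.28 = 15.4
- Comfort: 16.438 × (3.47 − 0.72)/3.47 = 13.0
- Bowel sounds: 7.334 × (2.12 − 0.76)/2.12 = 4.7

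All remain far beyond the 0.05 threshold.

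**The case for a change.** The strongest case for a change is that a common interval is a basic condition of a pre-test/post-test comparison with an untreated arm, and the text claims it without showing it. The post-test is fixed at 15 minutes after the last rinse, so a third 20-minute interval could only precede the first rinse, and no such wait is described. Every other route to 75 also needs something unstated. Starting the clock at the cognitive test fits poorly, because the control description places the 75 minutes after the forms and auscultation. A reader cannot tell whether controls were measured at the same time, 7 to 9 minutes later or 20 minutes later. A sentence of clarification would cost almost nothing.

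The point about reporting stands: equal timing is asserted and not demonstrated, and 3 × 20 + 15 could itself be a miscount. The step from there to a flaw does not hold.

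- The 66–68 minute figure applies the average response time of an eight-patient pilot, with unspecified coverage of the four tools, and sets rinse and waiting time to zero.
- The 20-minute excess needs the clock to start at the end of the first assessment, rinsing to begin at once and rinses to take no time. The order of a sentence does not define a clock origin.
- The claim of consistency may partly describe how the forms were given, not only when.

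**Conclusion.** No change follows. This is a missing timing detail, and filling it in would alter neither the design nor the analysis. The document's own numbers give 75 exactly when three full intervals are counted, and a mismatch of 0 to about 20 minutes is possible but not proven.

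At 20 minutes, linear control drift explains 1.2% to 2.5% of the reported differences, and at most about 10% at the unfavourable limit. Even if all of the control change at that limit fell in those 20 minutes, the smallest t value would be 4.7. These results assume a pre-post correlation between 0 and 0.8 and treat the adjustment as a fixed amount with the standard error unchanged.

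Elapsed time would not help as a covariate if each arm had one fixed interval, because it would then be indistinguishable from treatment. This covers timing only and says nothing about other possible sources of bias in the comparison.

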difference between the two groups was statistically significant ($t=-2.635$, $p=0.010$), indicating that patients in the experimental group began oral intake earlier than those in the control group. All patients in the experimental group started oral intake within 6–24 hours, whereas 88% of the control group started within 6–24 hours, 8% between 24–48 hours, and 4% after more than 48 hours. This difference was also statistically significant ($\chi^2=6.391$, $p=0.041$), again showing that oral intake began earlier in the experimental group.

Before mouth rinsing, the mean VAS Comfort Level score in the experimental group was 3.59 ± 1.29 , the mean Surgical Thirst Discomfort Scale (SPTDS) score was 8.00 ± 2.84 , and the mean number of bowel sounds was 3.49 ± 1.06 . In the control group, the initial mean VAS Comfort Level score was 4.02 ± 1.71 , the mean SPTDS score was 8.14 ± 2.74 , and the mean number of bowel sounds was 4.06 ± 1.52 . No significant differences were found between the groups in terms of VAS Comfort Level ($t=1.399$, $p=0.165$) or SPTDS ($t=-0.253$, $p=0.801$), indicating similar baseline comfort and thirst discomfort levels. However, the difference in bowel sound frequency was significant ($p<0.05$), favoring the control group, with a moderate effect size (Cohen's $d=0.44$).

After oral rinsing, the mean VAS Comfort Level score in the experimental group increased to 7.33 ± 1.14 , while in the control group's second measurement it was 3.86 ± 0.94 . This difference was statistically significant ($t=16.438$, $p<0.001$), demonstrating that oral rinsing significantly improved comfort, with a very large effect size (Cohen's $d=3.32$).

The mean SPTDS score decreased to 1.31 ± 1.54 in the experimental group after oral rinsing, compared to 8.59 ± 2.15 in the control group's second measurement. The difference was statistically significant ($t=-19.269$, $p<0.001$), indicating that oral rinsing significantly reduced thirst-related discomfort, with a very large effect size (Cohen's $d=3.89$).

The mean number of bowel sounds increased to 5.98 ± 1.61 in the experimental group after oral rinsing, whereas it was 3.86 ± 1.22 in the control group's second measurement. This difference was statistically significant ($t=7.334$, $p<0.001$), suggesting that oral rinsing enhanced bowel motility, with a large effect size (Cohen's $d=1.48$).

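### The claim that all data met the ±1.96 skewness-kurtosis rule cannot be true for two control-group variables, and the oral-intake comparison does not match its own printed figures

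*Combined protocol and SAP*

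**What the plan says.** The Data Analysis section gives the rule: "A Skewness-Kurtosis value between +1.96 and -1.96 is considered a normal distribution". It then states without exception: "All data used in the study were within the normal range, and the data showed a normal distribution". The t-tests and repeated-measures ANOVA are listed next.

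The RESULTS section describes two control-group variables as follows.

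- Time to start oral intake after surgery: "in the control group it ranged between 2–66 hours, with a mean of 15.20 ± 11.57 hours". The experimental group has 10.41 ± 4.64 h, range 6 to 20 h.
- Preoperative fasting time: "between 8–36 hours in the control group, with a mean of 12.78 ± 4.33 hours".

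Oral-intake time is compared twice. The t-test is printed as t=-2.635, p=0.010. The categorical test is printed as chi-square 6.391, p=0.041, with every experimental patient in the 6 to 24 h band and "88% of the control group started within 6–24 hours, 8% between 24–48 hours, and 4% after more than 48 hours". This second test is read as "again showing that oral intake began earlier in the experimental group".

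Under Data Collection Tools, both variables belong to the Personal Information Form, among the "clinical characteristics, including diagnosis, preoperative fasting time, postoperative oral intake time, and the time to start oral intake". Neither is an outcome named in the title. Study Population and Sample gives 49 patients per group.

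**The concern.** A maximum more than four SDs above the mean in a sample of 49 points to a heavy right tail, and both control variables have one. If the document's own rule fails for them, the unqualified normality sentence is false as printed. That sentence is the only support the document offers for using t-tests throughout.

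The consequence falls on oral-intake time, which was t-tested and interpreted as a benefit. In a distribution with a long tail, a mean difference can come from a few late patients and not from a shift in the whole group, and mean ± SD does not show which. Two further signs suggest that the figures for this variable were not checked against each other: the t value, and a minimum that lies below the lowest category.

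**Working it through.** **Inputs.** n=49 per group (Study Population and Sample); means, SDs, ranges, percentages and test results from RESULTS; the ±1.96 limit from Data Analysis. Sidedness is not stated; two-sided tests are assumed.

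**1. Lower bound on kurtosis.** SPSS reports

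G2 = [n(n+1)/((n-1)(n-2)(n-3))] × Σz⁴ − 3(n-1)²/((n-2)(n-3)), with z = (x − mean)/SD.

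At n=49 this is G2 = 0.023609 × Σz⁴ − 3.197. The z² values must sum to n−1=48. Fix one patient at the printed maximum. Σz⁴ is then smallest when the remaining z² is spread equally over the other 48, so Σz⁴ ≥ zmax⁴ + (48 − zmax²)²/48. Nothing is assumed about shape.

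| Control variable | zmax | zmax⁴ | Rest | G2 at least |
|---|---|---|---|---|
| Oral intake | (66−15.20)/11.57 = 4.39 | 371.6 | 17.2 | 5.98 |
| Fasting | (36−12.78)/4.33 = 5.36 | 827.0 | 7.7 | 16.5 |

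Rounding of the printed mean and SD moves these only to 5.96–6.00 and 16.4–16.6. If ±1.96 was meant for the statistic divided by its standard error (0.668 for kurtosis), the ratios are at least 9.0 and 24.7. Pooling both arms (n=98) does not help: the maximum alone forces kurtosis of at least 9.7 for oral intake and 18.9 for fasting.

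**2. Adding the other printed facts.** A linear program on a quarter-hour grid, holding the printed mean, SD, minimum and maximum, gives:

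- control oral intake with the 43/4/2 split (88%, 8% and 4% of 49): kurtosis 7.3 to 15.0, skewness 1.94 to 3.84;
- control fasting: kurtosis 16.5 to 27.9, skewness 2.97 to 5.29;
- experimental oral intake: kurtosis −1.83 to 0.79, skewness 0.16 to 1.65, so this arm can pass.

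For control oral intake the proven breach is in kurtosis, because skewness could just sit inside the limit. For control fasting both measures fail.

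**3. The t-test.** t = (10.41 − 15.20)/√((4.64² + 11.57²)/49) = −4.79/√3.171 = −2.690; p=0.008 (pooled, df 96) or 0.009 (Welch, df 63.1). With equal arms the two versions share the same t, so the choice between them cannot explain the gap. Moving every input by its rounding error gives −2.683 to −2.697. The printed −2.635 lies outside that range.

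**4. The categorical test.** The table 49/0/0 against 43/4/2 gives chi-square 6.391, p=0.041, exactly as printed. So the percentages use all 49 per group, and the t value alone fails to reproduce. Expected counts per row are 46, 2 and 1, so four of six cells are at 2 or 1. The exact (Fisher-Freeman-Halton) p is 0.027.

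**5. Minimum against categories.** 43 + 4 + 2 = 49 puts every control at 6 h or later. The printed control minimum is 2 h. Both cannot be right.

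**6. Where the mean difference comes from.** The control total is 49 × 15.20 = 744.8 h. The printed constraints put the mean of the 43 controls in the lowest category between 11.14 and 12.44 h, so the late six average (744.8 − 43 × 11.14)/6 = 44.3 h down to about 35.0 h. Their share of the 4.79 h difference is (6/49) × (mean of six − 10.41)/4.79, which is 0.63 at 35.0 h and 0.87 at 44.3 h.

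**The case against.** The strongest reply is that nothing of consequence changes. A t-test with 49 per arm tolerates a good deal of non-normality; Welch gives p=0.009, and the exact test gives a smaller p than the one printed. Oral-intake time is a form item and does not appear in the CONCLUSION. Fasting time is only described, with no between-group test reported. The post-rinse t values for comfort, thirst discomfort and bowel sounds reproduce within rounding at 49 per group. All of this stands and limits the weight of the point.

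A second reply is that the oral-intake bound rests on the printed 66 h, while this review questions the minimum of the same range. This is partly right: without that maximum, the mean, SD and 43/4/2 split would allow kurtosis below 0.5. The accurate statement is therefore that the sentence is incompatible with the figures as printed. Repairing t does not rescue it. Raising the control SD to about 11.85 to obtain −2.635 still leaves kurtosis at 5.2 or more, and 47 per group leaves at least 6.4. The fasting-time breach does not depend on the oral-intake figures at all.

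Third, the document does not say in words that the t-tests were chosen because the data were normal; that link is inferred from the order of the text. Reading the result as a late tail is also interpretation. The 63% to 87% share singles out the highest values in one arm, and the categorical difference arises after 24 h by construction. The share shows that the printed figures cannot establish a general shift; it does not show that there was none.

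**Conclusion.** The concern holds. Taking the printed mean, SD, maximum and n=49 as correct, the normality statement fails under its own rule for control oral-intake time (kurtosis at least 5.98, or 7.3 with the category split) and control fasting time (at least 16.5), against a limit of 1.96. The oral-intake t and p are not those implied by the printed summaries: −2.690 and 0.008 against −2.635 and 0.010. The 2 h minimum contradicts the categories.

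The 4.79 h difference in means is arithmetically correct, and significance at 0.05 survives every correction that can be computed. What a rank-based test would show is unknown without patient data. No ranges are printed for the thirst, comfort and bowel-sound measures, so nothing is shown about their distributions. This should be fixed because a stated property of the data and a reported statistic are wrong as printed, not because a main conclusion is overturned.

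**What to change.** - Delete or correct the blanket normality sentence, and state which variables met the rule in which group.
- Report median and IQR for oral-intake time and fasting time.
- Compare oral-intake time with a method that does not assume normality, such as Mann-Whitney (or van Elteren by diagnosis stratum), with a Hodges-Lehmann difference and confidence interval.
- Use an exact test for the three categories.
- Reconcile t=−2.635 with the means, SDs and group sizes. Any of these could be the misprint; as an illustration only, 47 per group would give −2.634, but no missing patients are reported.
- Reconcile the 2 h control minimum with a lowest category that starts at 6 h.
- Describe earlier oral intake as an exploratory observation.

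The cost is a rerun of two variables on data already collected, plus revised wording. No new data are needed.

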Unique Protocol ID: 2024-01/33

Official Title: Effect of Postoperative Oral Rinsing on Thirst-Related Discomfort, Comfort Level, and Bowel Movement in Individuals Undergoing Abdominal Surgery: A Randomized Controlled Trial

NCT ID not yet assigned

Date of Document: January 18, 2024

Study Design

This study was conducted as a randomized controlled trial with pre-test and post-test design, involving intervention and control groups.

Study Setting and Duration

The research was carried out at the Department of General Surgery, Sivas Cumhuriyet University Research and Training Hospital, between June 5 2024, and December 5, 2024.

Study Population and Sample

The study population included patients who underwent abdominal surgery in the general surgery clinic during the study period. The sample size was calculated using G*Power 3.1.9.7 software by a biostatistics expert. With an effect size of 0.50, $\alpha=0.05$, and power=0.85 ($\beta=0.15$), the required sample size was determined to be 82 patients (41 in the intervention group and 41 in the control group). The actual study was completed with 98 patients (49 per group), considering potential data loss. Eligible patients were stratified based on diagnosis and randomized using block randomization with a random number table in a 1:1 allocation ratio.

Inclusion and Exclusion Criteria

The study included patients who were able to communicate, aged 18 or older, agreed to participate, and were scheduled for elective surgery.

Patients were excluded if they were over 80 years old, had a mental disorder that prevented them from rinsing their mouth, were unconscious after surgery, were at risk of swallowing water during rinsing, and underwent emergency surgery.

Patients who refused to complete the post-test and those requiring intensive care after surgery were excluded.

Data Collection Tools

Four tools were used:

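### The between-group test uses neither the measured baselines nor the diagnosis strata; this matters mainly for bowel sounds, where the arms differed at baseline

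*Combined protocol and SAP*

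**What the plan says.** Study Population and Sample states that "Eligible patients were stratified based on diagnosis and randomized using block randomization with a random number table". Intervention Procedure explains that, after the pilot, "the data collection instruments were administered only before the first oral rinse and after the completion of all three rinses", so each outcome has one baseline and one post-test value.

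Data Analysis names three tests:
- between groups: "A t-test for independent samples was used to determine the mean differences between two independent groups";
- within groups: "a t-test for dependent samples was used to compare pre- and post-intervention measurements";
- in addition: "a single-factor analysis of variance (ANOVA) was used for repeated measures".

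No covariate, stratum term or group-by-time term appears. Results says of the baseline that "the difference in bowel sound frequency was significant", with the higher mean in control. It then reports the post-test bowel-sound comparison as "suggesting that oral rinsing enhanced bowel motility, with a large effect size" and does not return to the imbalance. The closing summary of Results sets improvement in the experimental arm against the control arm: "while no meaningful changes occurred in the control group".

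**The concern.** When an outcome is measured before and after treatment, the baseline usually predicts part of the post-test value. A post-test t-test leaves that information out. It is unbiased over repeated randomisations, but in this sample the control arm started 0.57 bowel sounds higher. If baseline and post-test values are positively correlated, the raw difference is then too small, by the within-arm slope times 0.57. Unless the correlation is low, its confidence interval is also wider than it need be. The same design logic applies to diagnosis: a factor used to stratify the randomisation would normally be in the analysis model.

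Neither of the other two named methods fills the gap. The repeated-measures ANOVA as described has no group term, and with two time points in one arm it repeats the paired t-test (F = t²). No ANOVA result is reported. Setting a change in one arm against no significant change in the other is not a test of the difference between arms, although Results does report between-group tests separately.

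At stake are the size and precision of the effects on which the Conclusion rests its recommendation for routine care.

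**Working it through.** **Inputs** (Results; n=49 per arm from Study Population and Sample), mean (SD):

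| Outcome | Baseline, exp. | Baseline, control | Post, exp. | Post, control |
|---|---|---|---|---|
| Bowel sounds | 3.49 (1.06) | 4.06 (1.52) | 5.98 (1.61) | 3.86 (1.22) |
| VAS comfort | 3.59 (1.29) | 4.02 (1.71) | 7.33 (1.14) | 3.86 (0.94) |
| SPTDS | 8.00 (2.84) | 8.14 (2.74) | 1.31 (1.54) | 8.59 (2.15) |

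**Step 1: reproduce the reported tests.** t = difference / √((SD_E² + SD_C²)/49).
- Bowel sounds: 2.12/0.2886 = 7.35 (reported 7.334).
- Comfort: 3.47/0.2111 = 16.44 (reported 16.438).
- SPTDS: −7.28/0.3778 = −19.27 (reported −19.269).

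These are raw post-test t-tests. The raw bowel-sound interval is 2.12 ± 1.985 × 0.2886 = 1.55 to 2.69.

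**Step 2: baseline bowel sounds.** t = −0.57/√((1.06² + 1.52²)/49) = −2.153, p=0.034, d=0.435. This agrees with the reported significant difference and d=0.44.

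**Step 3: rebuild the ANCOVA.** The within-arm pre-post correlation r is not reported. I assume the same r in both arms and vary it.
- Sxx = 48(SDpre_E² + SDpre_C²)
- Sxy = 48r(SDpre_E·SDpost_E + SDpre_C·SDpost_C)
- Syy = 48(SDpost_E² + SDpost_C²)
- slope b = Sxy/Sxx
- adjusted difference = raw difference − b × baseline difference
- s² = (Syy − Sxy²/Sxx)/95
- SE = √(s²(2/49 + (baseline difference)²/Sxx))

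Bowel sounds at r=0.5: Sxx = 164.83, Sxy = 85.46, Syy = 195.86 and b = 0.518. The adjusted difference is 2.12 + 0.518 × 0.57 = 2.42. Then s² = (195.86 − 44.31)/95 = 1.595 and SE = 0.261, so the 95% CI is 1.90 to 2.93.

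Bowel sounds over the range of r (raw 2.12, SE 0.289):

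| r | b | Adjusted difference (95% CI) | Shift | SE |
|---|---|---|---|---|
| 0 | 0 | 2.12 (1.53 to 2.71) | 0 | 0.297 |
| 0.2 | 0.207 | 2.24 (1.66 to 2.82) | 0.12 | 0.292 |
| 0.3 | 0.311 | 2.30 (1.73 to 2.86) | 0.18 | 0.285 |
| 0.5 | 0.518 | 2.42 (1.90 to 2.93) | 0.30 | 0.261 |
| 0.7 | 0.726 | 2.53 (2.09 to 2.97) | 0.41 | 0.222 |

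The adjusted SE falls below the raw SE only when r exceeds about 0.25. A negative r would move the estimate the other way: at r=−0.5 it is 1.82 (1.31 to 2.34).

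**Step 4: the other two outcomes, at r=0.3, 0.5 and 0.7.**
- Comfort: 3.47 becomes 3.56, 3.61 and 3.67, with the SE about 3%, 11% and 26% smaller (break-even r about 0.18).
- SPTDS: −7.28 becomes −7.25, −7.23 and −7.22, with the SE about 4%, 12% and 27% smaller (break-even r about 0.11).

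**Step 5: strata.** No outcome data by diagnosis are given, so the effect of adding the stratum term cannot be computed.

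**The case against.** The strongest reply is that this is a question of efficiency and changes no conclusion. The raw comparison is unbiased under randomisation, and the imbalance runs against the intervention, so with a positive r the reported bowel-sound effect is conservative. The illustrated shifts (0.18 to 0.41) all lie within the raw interval's half-width of 0.57. This stands, and it is why the point is an improvement to make and not a fatal flaw.

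The size of the gain also depends on an unknown r, and on r being equal in the two arms. Equal r with these SDs implies unequal bowel-sound slopes: at r=0.5, 0.5 × 1.61/1.06 = 0.76 in the experimental arm against 0.5 × 1.22/1.52 = 0.40 in control. With r=0 in the experimental arm and 0.5 in control, the same formulas give 2.27 with SE 0.288, so a shift of 0.15 and almost no gain in precision. For SPTDS the experimental post-test mean of 1.31 is close to the floor of a 0 to 12 scale, so the correlation there may be weak and the SE reductions above optimistic. These points limit the gain but do not favour leaving the baseline out, and the patient-level data would settle them.

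A significant baseline test is a poor reason to adjust, and a model chosen after the results are known is post hoc. Both are right. The case for adjustment rests on the design (a measured baseline and a stratified randomisation), applies to all three outcomes, and must be labelled post hoc. Finally, the diagnosis categories and block size are not described, and some strata may be sparse. That affects how the stratum term is specified.

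**Conclusion.** The concern holds. The between-group analysis is an unadjusted post-test t-test for every outcome, confirmed by reproducing the reported t values. For bowel sounds, the one outcome with a significant baseline difference, the raw 2.12 would become about 2.30 to 2.53 (8% to 19% larger), with an SE about 1% to 23% smaller, if r lies between 0.3 and 0.7 and is equal in both arms. At r=0 there is no shift, and below about r=0.25 the SE is slightly larger. Comfort moves by at most 0.20 and SPTDS by at most 0.06 (unrounded) over r=0.3 to 0.7. Direction and significance are unchanged for all three outcomes at every correlation tried. The contribution of the strata is unknown. The redundant ANOVA and the within-arm contrast are secondary wording faults; the between-group inference does not rest on them.

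**What to change.** For each of the three outcomes, fit an ANCOVA of the post-test value on group, that outcome's own baseline and diagnosis stratum. Report the adjusted difference with its 95% CI. Because results already exist, label this a post hoc revision and show it beside the original t-tests. Report the pre-post correlation in each arm, define the diagnosis strata, and state a rule for combining sparse ones before fitting. In Data Analysis, drop the single-factor repeated-measures ANOVA and keep the paired tests as description only. In the closing paragraphs of Results, rest the summary on the adjusted between-group differences and not on change in one arm against no significant change in the other.

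The cost is three models on patient-level data already collected, plus rewording of Data Analysis and Results. No new data are needed.
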